5.6.2 Hematological dose limiting toxicity

- a) In patients evaluable for hematological toxicity (see [section 4.1.7.1](#)), hematological dose limiting toxicity is defined as:

- Day 15:
 - o Grade 4 neutropenia or Grade 3 thrombocytopenia (platelets < 50,000/mm³) that does not resolve to ANC ≥ 500/mm³ and platelets ≥ 50,000/mm³ (transfusion independent) by Day 18 will be considered dose-limiting (See [Section 6.2.1](#)).
- Platelet count < 25,000/mm³ on 2 separate days, or requiring a platelet transfusion on 2 separate days, within a 7 day period
- Myelosuppression that causes a delay of > 14 days between treatment cycles.

- b) Note: Grade 3 or 4 febrile neutropenia will not be considered a dose-limiting toxicity.

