6.1 Dose Modification for Day 1 Dosing

6.1.1 Dose Modifications for Hematologic Toxicity

6.1.1.1 Patients who have dose-limiting thrombocytopenia should receive subsequent cycles at the next lower dose level.

6.1.1.2 Patients who have dose-limiting neutropenia with no other dose-limiting toxicity should receive the same dose in the next cycle with myeloid growth factor support or receive study drug at the next lower dose level. [Note: Patients MUST NOT receive prophylactic myeloid growth factor in the first cycle of therapy (See [Section 7.4](#)).] If dose-limiting neutropenia recurs after myeloid growth factor is added, then the patient should be given the next lower dose level for subsequent cycles. If dose-limiting neutropenia recurs in a patient that has received a dose level reduction but has not received myeloid growth factor, then myeloid growth factor should be administered. If, per the treating physician, addition of myeloid growth factor is not in the best interest of the patient, the patient should be removed from protocol therapy. In the case where myeloid growth factor is used, it should be initiated 24 hours after the dose. If the day 15 dose is delayed to allow for recovery, the myeloid growth factor should not be given until 24 hours after the day 15 dose is given. If the day 15 dose is omitted, myeloid growth factor can be given at the time the decision is made to omit the dose.

THIS PROTOCOL IS FOR RESEARCH PURPOSES ONLY, SEE PAGE 1 FOR USAGE POLICY

6.1.1.3 Patients who experience dose-limiting thrombocytopenia after one dose reduction or dose-limiting neutropenia after addition of myeloid growth factor and one dose reduction must be removed from protocol therapy.

6.1.1.4 Patients who have a dose-limiting hematological toxicity that does not resolve to eligibility parameters within 21 days after the planned start of the next treatment cycle must be removed from protocol therapy.

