6.1.2 Dose Modifications for Non-Hematological Toxicity

6.1.2.1 Patients who have any dose-limiting non-hematological toxicity (as defined in [Section 5.5.1](#)) may continue on protocol therapy upon meeting eligibility lab requirements or baseline but should receive subsequent doses at the next lower dose level.

6.1.2.2 If the patient experiences non-hematological dose-limiting toxicity after one dose reduction, the patient must be removed from protocol therapy.

6.1.2.3 Patients who have a dose-limiting non-hematological toxicity that does not resolve to baseline or eligibility (whichever is higher) within 21 days after the planned start of the next treatment cycle must be removed from protocol therapy.

6.2 **Dose Modifications for Day 15 Dosing due to Toxicity on Day 15.**

6.2.1 Dose Modifications for Hematological Toxicity:

6.2.1.1 Patients who have Grade 4 neutropenia or Grade 3 thrombocytopenia (platelets < 50,000/mm³) on Day 15 will have their dose withheld. If the toxicity resolves to ANC \geq 500/mm³ and platelets \geq 50,000/mm³ (transfusion independent) by Day 18, the dose may be given. Platelets cannot be given to achieve a platelet count >50,000/mm³ to receive the day 15 dose. If the toxicity does not resolve to ANC \geq 500/mm³ and platelets \geq 50,000/mm³ by Day 18, the dose will be omitted and this will be considered a DLT. Patients who require that their Day 15 dose be omitted for Grade 4 neutropenia or Grade 3 platelets (< 50,000/mm³) after a dose reduction for any reason must be removed from protocol therapy.

6.2.1.2 Patients who meet hematological DLT criteria as defined in [Section 5.5.2](#) on Day 15 will have their Day 15 dose omitted. Patients should receive subsequent cycles of drug per [Section 6.2](#) after their toxicity resolves, no sooner than the planned start of the subsequent cycle. Patients who require that their Day 15 dose be omitted for hematologic DLT as defined in [Section 5.5.1](#) after one dose reduction must be removed from protocol therapy.

6.2.2 Dose Modifications for Non-Hematologic Toxicity:

6.2.2.1 Patients who have Grade 3 or Grade 4 non-hematological toxicity attributable to the study drug prior to the Day 15 dose (with the exception

THIS PROTOCOL IS FOR RESEARCH PURPOSES ONLY, SEE PAGE 1 FOR USAGE POLICY

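### When a platelet DLT is already met by Day 15, 6.2.1.1 permits the Day 15 dose and 6.2.1.2 omits it, with no precedence stated; related cross-references in Section 6 are also wrong

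*Combined protocol and SAP*

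**What the plan says.** All references are to the combined protocol and SAP.

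- **5.6.2, hematologic DLT.** One criterion is "Platelet count < 25,000/mm³ on 2 separate days, or requiring a platelet transfusion on 2 separate days, within a 7 day period". It does not depend on what happens between Day 15 and Day 18. A separate Day 15 bullet makes Grade 4 neutropenia or platelets below 50,000/mm³ dose-limiting only if unresolved by Day 18.
- **6.2.1.1, Day 15.** "Patients who have Grade 4 neutropenia or Grade 3 thrombocytopenia (platelets < 50,000/mm³) on Day 15 will have their dose withheld". On recovery to the stated counts, "transfusion independent) by Day 18, the dose may be given". The clause states no dose level for that dose and does not exclude patients who already meet a DLT. Without recovery by Day 18, the dose is omitted and the event is a DLT.
- **6.2.1.2, Day 15.** Patients who meet hematologic DLT criteria "on Day 15 will have their Day 15 dose omitted. Patients should receive subsequent cycles of drug per" the rules of Section 6.2. The next cycle waits until the toxicity has settled and may not begin before its scheduled date. There is no Day 18 recovery option. A last sentence requires removal if the omission follows an earlier dose reduction.
- **6.1.1.1, Day 1 dosing.** "Patients who have dose-limiting thrombocytopenia should receive subsequent cycles at the next lower dose level".
- **6.2.2.2.** For non-hematologic toxicity, this clause also refers dose modification in later cycles to Section 6.2.
- **DLT references.** 6.2.1.2 cites 5.5.2 for the hematologic DLT and then 5.5.1 for the same DLT in its removal sentence. 6.2.2.2 cites 5.5.2 for the non-hematologic exclusions. Section 5.5 is now adverse event grading; the definitions are in 5.6.1 (non-hematologic) and 5.6.2 (hematologic).

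**The concern.** A dose-modification section should give one action for one clinical state. Here two adjacent clauses can describe the same patient on the same day and lead to different actions, after a thrombocytopenia severe enough to be dose-limiting. Two sites could each follow a clause as written and give a different number of doses in that cycle.

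The reader who then looks for the next-cycle dose is sent back to the section already being read. The one who looks for the DLT definition is sent to numbers that no longer hold it. None of this bears on sample size or error rates. At stake are uniform handling of a safety event and a clear audit standard for Day 15 dosing.

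**Working it through.** The plan gives no figure to reproduce, so the check is whether the clauses can both apply, and what follows if they do.

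**Step 1. Can the platelet DLT be met by Day 15?** Section 8.1 schedules blood counts twice weekly (every 3 to 4 days) in Cycle 1, so two counts fall within 7 days before or on Day 15. In later cycles the scheduled counts are on Day 1 and Day 15, which are 14 days apart. Two scheduled counts then cannot fall in one 7-day window, and the two-count route needs unscheduled counts. The overlap is therefore mainly a Cycle 1 matter.

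**Step 2. Can both clauses apply to one patient?** Illustrative counts of 20, 40 or 60 thousand on Days 8, 12, 15 and 18 give 3⁴ = 81 patterns. The DLT is taken as met when two counts below 25 thousand, on Day 15 or earlier, lie less than 7 days apart.

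| Situation | Patterns |
|---|---|
| DLT met, Day 15 below 50, Day 18 at least 50: both clauses apply and differ | 4 |
| DLT met, Day 15 at least 50: only 6.2.1.2 applies | 3 |
| No such DLT, Day 15 below 50, Day 18 at least 50: only 6.2.1.1 applies | 14 |

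The four conflicting patterns (Days 8, 12, 15, 18; thousands) are 20-20-20-60, 20-20-40-60, 40-20-20-60 and 60-20-20-60. In three of them the Day 15 count is itself below 25 thousand. In 20-20-40-60 the DLT was complete on Day 12, so the conflict needs 6.2.1.2 to be read as covering a DLT met by Day 15. The counts show that the overlap is reachable; they are not probabilities.

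**Step 3. The transfusion route.** Two transfusion days meet the DLT, but 6.2.1.1 is triggered for platelets only if the Day 15 count is also below 50,000/mm³. Recovery must be transfusion independent. The only definition, given for eligibility in 4.1.7.1, is no platelet transfusion for at least 7 days. If it carries over, the last transfusion can be no later than Day 18 − 7 = Day 11; after a later one, both clauses omit the dose.

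**Step 4. What differs on Day 15.** Under 6.2.1.2 a patient at the 20 mg/kg level receives one dose in the cycle. Under 6.2.1.1 the patient may receive two. If the second were given at the same level, the administered total would be 20 + 20 = 40 mg/kg against 20 mg/kg; 6.2.1.1 does not state the level.

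**Step 5. The next cycle.** Section 6.2 is titled "Dose Modifications for Day 15 Dosing due to Toxicity on Day 15". After a hematologic DLT it gives the timing of the next cycle and a removal rule, but no dose level. Section 6.1.1.1 gives the level for dose-limiting thrombocytopenia, with no exception for events seen on Day 15.

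**Step 6. DLT references.** 6.1.2.1 and 6.2.2.1 cite 5.5.1 for non-hematologic toxicity, and the first sentence of 6.2.1.2 cites 5.5.2 for hematologic toxicity. This fits a former numbering in the same order as today's 5.6.1 and 5.6.2. On that inference, the removal sentence of 6.2.1.2 (hematologic, cites 5.5.1) and 6.2.2.2 (non-hematologic, cites 5.5.2) each point to the opposite class.

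**The case against.** **The clauses can be read together.** 6.2.1.1 is permissive and 6.2.1.2 is mandatory and specific to patients with a DLT. Omitting the dose breaches neither; giving it breaches 6.2.1.2. The Day 15 bullet of 5.6.2 refers to 6.2.1 for counts that become a DLT only if unresolved by Day 18, which suggests separate scopes. This is a reasonable reading, and it means patients *can* be handled differently, not that they will be. But 6.2.1.1 has no carve-out and no clause states precedence, so the reader must supply the rule.

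**A reader might infer that the next-cycle dose is undefined, or that an unreduced next cycle is allowed.** The documents do not support this. 6.1.1.1 applies on its own terms, and nothing lets the circular reference in 6.2.1.2 cancel it.

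**A reader might infer that exposure doubles.** The ratio of 2 concerns administered dose, at an unchanged level. Assume first-order elimination, equal doses on Days 1 and 18, and the 20 mg/kg half-life of 20 ± 5 days in 2.3.3. The 28-day AUC ratio is then 1 + (1 − e^(−11k))/(1 − e^(−28k)), with k = ln 2 / half-life. For 20 days this is 1 + 0.317/0.621 = 1.51; for 15 and 25 days it is 1.55 and 1.49.

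**Reach and safeguards.** Thrombocytopenia is not in the toxicity table (9.1.8). Adult treatment-related events were Grade 1 or 2 except one Grade 3 GGT elevation (2.3.1), and the first six Part A patients had no DLT (2.5). DLTs go to the Study Chair within 24 hours (5.5), dosage modifications are notified (6.0), and data are reviewed weekly (14.3). All of this stands and makes the practical effect small. It does not settle what the text requires.

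**The stale numbers mislead few readers.** The words around them name the toxicity class, and 6.1.1.3 independently requires removal for dose-limiting thrombocytopenia after one reduction. That also stands; the references are still wrong.

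**Conclusion.** The point holds in limited form. For a patient who meets the 5.6.2 platelet DLT by Day 15, has platelets below 50,000/mm³ on Day 15 and recovers, transfusion independent, by Day 18, 6.2.1.1 permits the Day 15 dose and 6.2.1.2 omits it. No precedence is stated, so the cycle can contain one dose or two.

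The affected group is very small. Its size cannot be computed from the documents, and it shrinks further if the 7-day meaning of transfusion independence carries over from eligibility. The event is a DLT under 5.6.2 whichever clause is followed, so DLT counts, and the Part A and Part B rules that use them, are unaffected.

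The subsequent-cycle references in 6.2.1.2 and 6.2.2.2 are erroneous cross-references, not a missing rule. The 5.5.1 and 5.5.2 citations are stale. That two of them point to the opposite class rests on the inferred former numbering.

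**What to change.** 1. Reconcile 6.2.1.1 with 6.2.1.2 by stating which governs when a 5.6.2 DLT is already met on Day 15, and whether a DLT completed before Day 15 counts as met on that day. If the Day 15 dose can be given in this situation, state its level. These are the sponsor's clinical decisions, and this review proposes none.
2. State whether the eligibility meaning of transfusion independence applies in 6.2.1.1.
3. Reconcile the subsequent-cycle references in 6.2.1.2 and 6.2.2.2 with the rules in 6.1.
4. Correct the DLT references in Section 6: 5.6.1 for non-hematologic and 5.6.2 for hematologic toxicity.

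The cost is protocol wording and cross-references. No change to sample size, assessments or data collection is needed.

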5.0 TREATMENT PROGRAM

5.1 Overview of Treatment Plan

Day 1	Day 15	Day 28
VX15/2503 IV	VX15/2503 IV	End of Cycle/Evaluation

VX15/2503 will be administered intravenously over 60 minutes on Days 1 and 15 of a 28 day cycle. Patients should be monitored for signs and symptoms of infusion reactions during the drug infusion and for 4 hours after completion of post-infusion flush (e.g., monitor vital signs every 15 minutes during VX15/2503 infusion and every 30 minutes thereafter). Precautions for anaphylaxis should be observed during VX15/2503 administration. Emergency resuscitation equipment and medications should be present for immediate use in the immediate area where patients are receiving their infusions. If a patient develops a \geq Grade 2 infusion related reaction, the infusion should be stopped and standard institutional guidelines for management of infusion reactions should be followed. Note: If the initial dose is well tolerated subsequent doses will required patients to be monitored for 1 hour after completion of post-infusion flush.

See Section [6.2.3](#) for management and dose modification guidelines for infusion related reactions. If there is no evidence of an infusion related reaction during the initial 2 infusions of VX15/2503, then no observation period is required for subsequent treatment cycles. In the event an infusion related reaction occurs thereafter, the four-hour observation period should be reinstated.

A cycle of therapy is considered to be 28 days. A cycle may be repeated for a total of 13 cycles, up to a total duration of therapy of approximately 12 months. As some of the correlatives require same-day shipping (see [Section 8.5](#)), caution should be paid to the day of the week therapy should start and drug infusion should occur so that correlative samples are able to be sent out for analysis without delay.

Drug doses should be adjusted based on weight measured within 7 days prior to the beginning of each cycle.

Update: With the release of Amendment #2A, the dose confirmation portion of the study is complete. Given this, Part B will be open to patients \geq 12 months and \leq 30 years of age with relapsed and refractory osteosarcoma once the initial 6 adult patients complete toxicity assessments per [Section 11.6](#).

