Grade 2 Rash, flushing, urticaria, dyspnea, drug fever \geq 38°C	
 • Stop infusion, begin an IV infusion of normal saline, and treat the subject with diphenhydramine 1 mg/kg with max 50 mg IV (or equivalent) and/or acetaminophen 10-15 mg/kg (max 1000 mg); remain at bedside and monitor patient until resolution of symptoms. Corticosteroid or bronchodilator therapy may also be administered as appropriate. • If the infusion is interrupted, then restart the infusion at 50% of the original infusion rate when symptoms resolve. Monitor patient closely. • If symptoms recur, then no further VX15/2503 will be administered at that visit. Administer diphenhydramine 1 mg/kg with max 50 mg IV (or equivalent), and remain at

THIS PROTOCOL IS FOR RESEARCH PURPOSES ONLY, SEE PAGE 1 FOR USAGE POLICY

	
bedside and monitor the patient until resolution of symptoms.
 
The following prophylactic premedications are recommended: diphenhydramine 1 mg/kg with max 50 mg IV (or equivalent) and acetaminophen (10-15 mg/kg, max 1000 mg) should be administered at least 30 minutes before additional VX15/2503 administrations. If clinically indicated, corticosteroids (recommended dose: 1-2 mg/kg/day methylprednisolone IV or equivalent) may be used.

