
Grade 3 or 4 Symptomatic bronchospasm with or without urticaria, allergy-related edema/angioedema, hypotension; Anaphylaxis
	
 • Immediately discontinue infusion of VX15/2503. • Begin an IV infusion of normal saline, and treat the subject as follows. Recommend bronchodilators, epinephrine 0.2 to 1 mg of a 1 mg/ml solution for subcutaneous administration, 0.1 to 0.25 mg of a 0.1 mg/ml solution injected slowly for IV administration, 0.01 mg/kg of 1:1000 dilution (0.01 ml/kg/dose) for intramuscular administration, and/or diphenhydramine 1 mg/kg with max 50 mg IV with 1-2 mg/kg/day methylprednisolone IV (or equivalent), as needed. • Patient should be monitored until the investigator is comfortable that the symptoms will not recur. • VX15/2503 will be permanently discontinued. 
Investigators should follow their institutional guidelines for the treatment of anaphylaxis. Remain at bedside and monitor patient until recovery from symptoms. In the case of late-occurring hypersensitivity symptoms (e.g., appearance of a localized or generalized pruritis within 1 week after treatment), symptomatic treatment may be given (e.g., oral antihistamine, or corticosteroids).

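### Subcutaneous and IV epinephrine doses for Grade 3/4 infusion reactions have no weight basis, although patients from 12 months of age are eligible

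*Combined protocol and SAP*

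**What the plan says.** The Grade 3 or 4 row of Section 6.2.3 lists epinephrine by three routes in one sentence:

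- subcutaneous (SC): "epinephrine 0.2 to 1 mg of a 1 mg/ml solution for subcutaneous administration"
- intravenous (IV): "0.1 to 0.25 mg of a 0.1 mg/ml solution injected slowly for IV administration"
- intramuscular (IM): "0.01 mg/kg of 1:1000 dilution (0.01 ml/kg/dose) for intramuscular administration"

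The same sentence gives diphenhydramine at 1 mg/kg (maximum 50 mg) and "1-2 mg/kg/day methylprednisolone IV (or equivalent), as needed". The row then adds: "Investigators should follow their institutional guidelines for the treatment of anaphylaxis".

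The lower-grade rows dose per kg throughout. The Grade 2 premedication, for example, is "diphenhydramine 1 mg/kg with max 50 mg IV (or equivalent) and acetaminophen (10-15 mg/kg, max 1000 mg"), with optional methylprednisolone at 1-2 mg/kg/day. Bronchodilators and saline carry no dose.

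Section 5.1 says that for a reaction of Grade 2 or above "standard institutional guidelines for management of infusion reactions should be followed", and that "Emergency resuscitation equipment and medications should be present for immediate use in the immediate area" where infusions are given. It also points sites to Section 6.2.3 for managing these reactions.

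On who is covered, Section 4.1.1 admits patients from 12 months to 21 years in Part A and, after expansion, from 12 months to 30 years in Part B. Section 2.5 opens the PK expansion cohort from 12 months. Section 4.1.7.2 has a creatinine limit for children aged 1 to under 2 years. Section 8.3.2 and Appendix II have a separate sampling schedule for patients of 10 kg or less.

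**The concern.** One cell has to serve both a toddler and a 30-year-old. For SC and IV epinephrine it prints the same milligram amounts for both. The SC range is also 5-fold wide, with no rule for which patient gets which end. The rest of the table is weight-based, so these two entries look like an oversight; the protocol gives no reason for them.

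Staff may read this text during a severe reaction in a small child. Section 9.1.8 lists infusion-related reaction as occurring in 4-20% of patients, without grade, and Section 2.4.1 reports no earlier pediatric trials of the agent. A severe reaction may be uncommon, but that is the event this row is written for.

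The SC entry is the main issue because it uses the same strength of solution as the IM entry. The IV entry has the same wording gap, but it uses a weaker solution and slow injection, and no IV overdose is claimed.

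**Working it through.** The protocol states no derived figure to reproduce here. The check has two parts: look for a weight basis for each drug dose in the table, then express the fixed doses per kg.

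**Weight basis of each numeric drug dose in Section 6.2.3**

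| Drug and route | Rows | Dose | Per kg? |
|---|---|---|---|
| Diphenhydramine | Grades 1, 2, 3/4 | 1 mg/kg, max 50 mg | Yes |
| Acetaminophen | Grades 1, 2 | 10-15 mg/kg, max 1000 mg | Yes |
| Methylprednisolone IV | Grades 2, 3/4 | 1-2 mg/kg/day | Yes |
| Epinephrine IM | Grade 3/4 | 0.01 mg/kg | Yes |
| Epinephrine SC | Grade 3/4 | 0.2-1 mg | **No** |
| Epinephrine IV | Grade 3/4 | 0.1-0.25 mg | **No** |

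**Same solution.** A 1:1000 dilution is 1 mg/ml, so the IM entry of 0.01 ml/kg is 0.01 mg/kg. SC and IM therefore use the same strength.

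**Formulas**, with body weight w in kg:

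- SC per kg = 0.2/w to 1/w
- IM dose = 0.01 × w mg
- SC/IM ratio = 0.2/(0.01w) to 1/(0.01w)
- IV/IM ratio = 0.1/(0.01w) to 0.25/(0.01w)

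The protocol gives no weight distribution. The 10 kg line reflects its own weight cut-off; the other weights are assumptions.

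| w (kg) | SC (mg/kg) | IM (mg) | SC/IM | IV/IM |
|---|---|---|---|---|
| 10 | 0.020 to 0.100 | 0.10 | 2 to 10 | 1 to 2.5 |
| 15 | 0.013 to 0.067 | 0.15 | 1.3 to 6.7 | 0.67 to 1.67 |
| 20 | 0.010 to 0.050 | 0.20 | 1 to 5 | 0.5 to 1.25 |
| 70 | 0.003 to 0.014 | 0.70 | 0.29 to 1.43 | 0.14 to 0.36 |

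**Crossover.** The lowest SC dose equals the IM dose at 0.2/0.01 = 20 kg. Below that weight, every dose in the SC range exceeds the IM dose.

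**Within one route.** A fixed dose gives a 10 kg child 70/10 = 7 times the per-kg amount of a 70 kg adult. For assumed adult weights of 50 to 90 kg the factor is 50/10 = 5 to 90/10 = 9. This avoids comparing routes, but it follows from any fixed dose.

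**Width of the SC range.** 1/0.2 = 5-fold.

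**The case against.** The strongest reply is that no inappropriate dose has been shown. Judging whether 0.2 mg SC is unsuitable for a 10 kg child needs a dosing reference that the documents do not contain. SC and IM doses need not be equal, and the 10-fold figure pairs the top of the range with a 10 kg child, which the text does not direct. This stands: the ratios are a scale check within the document. Even so, the low end of the range does not remove the discrepancy below 20 kg.

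The second reply is that the text is advisory. The drugs are recommended for use as needed, Sections 5.1 and 6.2.3 both send sites to institutional guidelines, and Section 7.3 points to the cooperative group's supportive-care guidelines. A per-kg IM option is in the same sentence, and resuscitation drugs must be at hand. These points lower the risk and could be read as placing local guidelines first. But the row's lead-in tells staff to treat in the way it sets out, no route is preferred, and nothing says which source prevails. If local guidelines are meant to govern, the fixed figures add only possible conflict for a small child.

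The third reply is that exposure is limited. Harm needs a patient under 20 kg, a Grade 3/4 reaction, the SC route, and use of this cell over local guidance. Section 2.3.1 reports that related adult events were Grade 1 or 2 apart from one GGT rise. That is fair, but it is adult experience. The number of small children is unknown: the up to 6 PK patients in Section 11.1, aimed at those under 12 years, are not a cap, because Part B is also open from 12 months.

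**Conclusion.** The concern holds. The SC and IV epinephrine entries are the only numeric drug doses in the table without a per-kg basis, and the row applies to patients from 12 months of age. Below 20 kg the whole SC range lies above the row's own IM dose; at 10 kg it is 2 to 10 times that dose.

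The textual inconsistency is certain. Clinical harm is not shown, and its likelihood cannot be estimated from the documents, which give neither a weight distribution nor a rate of severe reactions in children. This is a safety-wording point that should be fixed. It changes no endpoint, sample size, decision rule or analysis.

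**What to change.** Use one of two options:

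1. Delete the fixed SC and IV figures, leaving the per-kg IM entry and the referral to institutional anaphylaxis guidelines.
2. Have the sponsor's medical and pharmacy leads restate the SC and IV entries per kg with a maximum.

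The first is simpler and needs no new dosing decision. A maximum for the IM entry, which has none, is optional. Which dose is correct is for the clinical and pharmacy leads to decide.

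The cost is one table cell in the next amendment and a short memo to sites. Study drug, visits and analysis do not change.
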